	
 
advanced bladder/urothelial tumors that have progressed after first line treatment, or who are intolerant to first line treatment, or who are unable to receive first line treatment with cisplatin-based chemotherapy. Patients with clinically stable, known metastatic tumors to the CNS are eligible with Medical Monitor approval. CNS radiography is not required in the absence of suspicion for clinical involvement. Prior treatment with anti-PD-1/anti-PD-L1 therapy is prohibited is prohibited.
 
Patients with histologically and/or cytologically confirmed diagnosis of advanced NSCLC previously treated with anti-PD-1 or anti-PD-L1 therapy. Patients with clinically stable, known metastatic tumors to the CNS are eligible with Medical Monitor approval. CNS radiography is not required in the absence of advanced NSCLC previously treated with anti-PD-1 or anti-PD-L1 therapy. Patients with clinically stable, known metastatic tumors to the CNS are eligible with Medical Monitor approval. CNS radiography is not required in the absence of suspicion for clinical involvement.
 

Duration of Follow-Up	Subjects will be followed as per the Study Calendar. After a subject is removed or withdrawn from study treatment, the subject will be followed for up to 1 year or until death, whichever occurs first.
	Off-treatment data on OS will be updated every 6 months or until death, whichever occurs first. If a subject is removed from the study due to unacceptable AEs, the event(s) will be followed until resolution or stabilization of the AE(s). Subjects who respond and discontinue study treatment for reasons other than progressive disease (PD) should have response assessments and survival should be collected every 2 months until disease progression or death, whichever occurs first. After disease progression, data for survival should be collected every 6 months until death.
	Criteria for Removal from Study Treatment
	Study treatment can continue for subjects receiving clinical benefit, unless one or more withdrawal criteria are met, or at the subject's discretion, or if the study is terminated.
	1. Study Treatment Discontinuation
	Study treatment must be discontinued if:
	• There is evidence of disease progression. Subjects who have PD but who are continuing to derive clinical benefit in the opinion of the investigator may continue to receive study treatment.

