#### Phase 1/2 Study of APR-246 in Combination with Pembrolizumab in Subjects with Solid Tumor Malignancies

# Table 4. Study Calendar

Study Calendar	Screening a						Cycle 2 and Subsequent Cycles				End of	Long-	
Evaluation a	(28 days)	D1	D2	D3	D4	D8 b, e	D15 b, e	D1 c	D2	D3	D4		Term Follow- up s
Informed consent	×												
Medical history d	×												
Physical examination e	×	×						×				×	
Height	×												
Weight	×	×						×				×	
Vital signs e	×	×	×	×	×			×	×	×	×	×	
ECOG PS	×	×						×				×	
APR-246 f		×	×	×	×			×	×	×	×		
Pembrolizumab g				×						×			
Disease assessment h	×							× h				×	
Hematology i	×	×				×	×	×				×	
Serum chemistry j	×	×				×	×	×				×	
Pregnancy test k	×												
ECG 	×	×I	×I	×I	×I			×					
APR-246 PK sample m		×	×	×	×			×	×	×	×		
Archival tissue collection n	×												
Fresh tissue biopsy °	×							×					
Blood for biomarkers p	×	×						×				×	
Blood for PBMC q	×	×						×				×	
Clinical toxicity assessment		Starting at the time of study treatment initiation through 30 days after last dose t											
Concomitant medications		Reviewed throughout study											
Survival												×	×

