- I. Standard 12-lead ECGs in triplicate at screening, on Days 1–4 of Cycle 1 and on Days 1 of each subsequent cycle with subject in a semi-recumbent position. Please consult Table 6 for ECG collection schedule.
- m. Please consult Section 8.5 for PK collection schedule.
- n. Tumor block or 20 unstained, 4-µm thick, paraffine-embedded tumor slides from an archival tissue sample, if available.

- Optional: Percutaneous or endoscopic biopsy of a tumor lesion will be only performed at baseline (within 2 weeks prior to treatment initiation) and at Cycle 2 Day 1 (±5 days). Biopsy samples will be formalin-fixed, paraffin embedded and snap frozen.
- p. Blood for serum analysis is collected on specific 5-mL dry tubes at screening, prior to treatment initiation at Cycle 1 Day 1, and at the time of second tumor biopsy/or prior to Cycle 2 Day 1 treatment if no biopsy is done.
- q. Blood for PBMC isolation is collected in four 10-mL CPT tubes (total, 40 mL) at screening, prior to treatment initiation at Cycle 1 Day 1, and at the time of second tumor biopsy/or prior to Cycle 2 Day 1 treatment, if no biopsy is done. Additional PBMCs will be collected prior to Cycle 5 Day 1 treatment and 30 days after treatment discontinuation.
- r. Subjects discontinuing treatment should complete their end of treatment visit 30 days after their last dose of APR-246. Physical exam, vital signs, clinical toxicity assessment, hematology, serum chemistry and disease assessment should be performed, if feasible.
- s. Long-term follow up can be done remotely (e.g. via telephone, via local practitioner or via review of medical records). Assuming there is no withdrawal of consent, subjects who stop study treatment for any reason (e.g. toxicity, PD) will continue long-term follow-up (see Section 7.4). If a subject is removed from the study due to unacceptable AEs, the event(s) will be followed until resolution or stabilization of the AE.
- t. AE description, grade and start date and resolution date should be documented.

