# 7.4 Long-Term Follow-Up

Long-term follow-up can be done remotely (e.g. via telephone, via local practitioner or via review of medical records). After a subject is removed or withdrawn from the study, the subject will be followed for 1 year or until death, whichever occurs first. Off-treatment data on OS will be updated every 6 months or until death, whichever occurs first. If a subject is removed from the study due to unacceptable AEs, the event(s) will be followed until resolution or stabilization of the AE(s). Subjects who respond and discontinue study treatment for reasons other than PD should have response assessments and survival should be collected every 2 months until disease progression or death, whichever occurs first. After disease progression, data for survival should be collected every 6 months until death.

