# 8.2 Efficacy Assessments

Tumor assessments will be performed by the investigators based on RECIST 1.1, which will also guide treatment decisions. All scans for tumor assessments performed during the study should be archived in accordance with the standard local practice. The scans must be accessible in the event of a Sponsor request to submit them for central review.

Tumor assessments will be carried out every 9 weeks (±3 days) after initiating study treatment, prior to initiation of each odd treatment cycle starting at Week 9, then every 6 weeks through the first year and then every 9 weeks, thereafter. CT/MRI scans of chest, abdomen, and pelvis and of other known sites of disease will be obtained at screening (within 28 days prior to Cycle 1 Day 1), at all tumor assessment time points, and as indicated clinically. Color photographs containing a millimeter scale must be taken of all skin lesions being used as target lesions. Historical standard of care scans that are performed with scanning parameters consistent with the requirements for this protocol within 28 days prior to dosing are acceptable. Subjects with squamous cell carcinoma of the head and neck must also have head and neck scans performed.

MRI may be used instead of CT for head, neck, abdomen, and pelvis; however, the chest must be assessed using CT. Chest disease may not be followed using chest x-ray. PET scanning should not be used, but PET/CT may be used if CT component is with contrast enhancement and of diagnostic quality.

A brain scan (CT with contrast or MRI pre- and post-gadolinium) must be performed at screening to assess potential CNS disease and/or metastases for patients with predilections to develop CNS metastases. For subjects with previously treated eligible brain metastases, a brain scan must be performed at all tumor assessment time points. For all subjects, a follow-up brain scan must be performed to confirm CR within 1 week of response confirmation, or if clinically indicated.

The tumor assessment schedule should not be affected by interruptions in study treatment.

Subjects taken off study treatment without disease progression will also undergo tumor assessments per the Study Calendar (Table 4) until disease progression is documented or another anticancer therapy is initiated.

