#### 8.2.4 Durable Stable Disease Rate

Durable SD rate is defined as the proportion of subjects whose BOR is SD and the duration of SD is  $\geq$  23 weeks.

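### Section 8.2 requires tumor assessments in every subject who stops treatment without progression, but Section 7.4 and the synopsis require them only in responders, so durable SD and CBR can be undercounted

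*Combined protocol and SAP*

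**What the plan says.** - **Section 8.2 (Efficacy Assessments):** "Subjects taken off study treatment without disease progression will also undergo tumor assessments per the Study Calendar (Table 4) until disease progression is documented". Starting a new anticancer therapy also ends these assessments. The rule does not depend on response, so it includes SD.
- **Section 7.4 (Long-Term Follow-Up):** "Subjects who respond and discontinue study treatment for reasons other than PD should have response assessments", at two-month intervals, ending at progression or death. SD is not mentioned.
- **Synopsis (Duration of Follow-Up):** the same restriction. "Subjects who respond and discontinue study treatment for reasons other than progressive disease (PD) should have" response assessments on the same terms as in 7.4.
- **Table 4 (Study Calendar):** the row "Disease assessment" is marked at screening, on Day 1 from Cycle 2 onward and at End of Treatment. In the Long-Term Follow-up column it is blank for everyone; only survival is marked there.
- **Footnote r:** the End of Treatment visit comes 30 days after the last APR-246 dose, and "hematology, serum chemistry and disease assessment should be performed, if feasible".
- **Footnote s:** "Long-term follow up can be done remotely (e.g. via telephone, via local practitioner or via review of medical records"). It refers sites to Section 7.4 for everyone who stops treatment.
- **Sections 8.2.4 and 8.2.5:** "Durable SD rate is defined as the proportion of subjects whose BOR is SD and the duration of SD is" at least 23 weeks. CBR adds CR and PR to durable SD.
- **Section 8.3:** PFS runs from first dose to first documented confirmed progression or death. No censoring rule is given.

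**The concern.** Section 8.2 relies on a calendar that is empty after End of Treatment, and the calendar refers the site to a rule for responders only. Two sites can therefore each follow a section of the protocol and treat the same SD subject differently: one keeps scanning, the other stops after the End of Treatment visit.

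Durable SD is affected most directly. It requires a best response of SD, so only non-responders can qualify, and they are the group that 7.4 leaves out. CBR inherits any undercount. For PFS, progression after End of Treatment is sought on a schedule in responders and not in SD subjects. Scans that were not taken cannot be recovered at analysis.

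**Working it through.** No figure in the plan rests on this point, so there is none to reproduce. The check uses the protocol's own schedule.

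**Inputs from the documents.** 21-day cycles with APR-246 on Days 1–4 (Section 6.1); End of Treatment visit 30 days after the last APR-246 dose (Table 4, footnote r); first scan at Week 9, then every 6 weeks in the first year (Section 8.2); durable SD threshold of 23 weeks (Section 8.2.4); at least 20 evaluable patients per cohort (Section 9.1).

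**Assumptions.** No dose delays, and Day 4 is given in the last cycle. SD duration is counted from first dose; Section 8.2 counts its 5-week minimum for SD that way, but the start of the 23 weeks is not defined. A later start would make the loss larger.

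**Step 1: the threshold.** 23 × 7 = 161 days.

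**Step 2: day of the End of Treatment scan.** If the last cycle is *c*, days since first dose = 21 × (*c* − 1) + 3 + 30.

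| Last cycle | Day | Weeks | Reaches day 161? |
|---|---|---|---|
| 6 | 105 + 33 = 138 | 19.7 | No |
| 7 | 126 + 33 = 159 | 22.7 | No, by 2 days |
| 8 | 147 + 33 = 180 | 25.7 | Yes |

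A visit 2 or 3 days late after Cycle 7, within the ±3-day window of footnote a, would just reach the threshold. Hence *about* Cycle 7.

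**Step 3: the two rules after that visit.** Under 8.2, scans fall at Weeks 9, 15, 21, 27 and so on, and Week 27 is the first at or beyond Week 23. Under 7.4 an SD subject has none. Section 8.2 and footnote h also tie scans to odd cycles, which does not fit Week 9: that precedes Cycle 4 (9/3 + 1). An odd-cycle reading would put the scan before Cycle 9, at Week 24. Either date falls after the End of Treatment visit of someone stopping at Cycle 7, so the result is unchanged.

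**Step 4: size.** One subject in 20 is 1/20 = 5 points. At the other sizes in Table 7 it is 1/30 = 3.3 and 1/40 = 2.5 points. For scale, assume 20 subjects, 4 responders and 4 with true durable SD (assumed counts, not in the documents), with a subject whose SD cannot be shown to last 23 weeks counted as not qualifying. Intervals are 95% Clopper–Pearson, the plan's method; the same calculation reproduces all six intervals in Table 7.

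| Missed | Durable SD | CBR |
|---|---|---|
| 0 | 4/20 = 20% (5.7–43.7) | 8/20 = 40% (19.1–63.9) |
| 1 | 3/20 = 15% (3.2–37.9) | 7/20 = 35% (15.4–59.2) |
| 2 | 2/20 = 10% (1.2–31.7) | 6/20 = 30% (11.9–54.3) |

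**Step 5: responders.** The rules differ for them too. Two months is 2 × 30.44/7 = 8.7 weeks under 7.4, against 6 weeks in year 1 and 9 weeks thereafter under 8.2. The end point is progression or death under 7.4, and progression or new anticancer therapy under 8.2.

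**The case against.** The strongest reply is that 8.2 already requires the scans, so a site that follows it loses nothing. Footnote h counts scans from treatment initiation and is not expressly limited to subjects on treatment. Both points are correct and make the harm conditional. They do not remove it: footnote h is also tied to treatment cycles, and footnote s points to 7.4.

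Three stronger readings are tempting, and the documents do not support them.

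- **That PFS will read too long.** This requires an unscanned subject to stay at risk until death and then count as an event. The documents neither say so nor say that such a subject is censored at the last scan; the synopsis leaves analysis detail to the SAP. With censoring at the last scan and stopping unrelated to prognosis, Kaplan–Meier is not biased by these subjects and only loses information. Stopping related to prognosis could bias PFS, but the documents give no basis for its direction or size.
- **That an SD subject who stops can only have death as a PFS event.** Every subject has an End of Treatment disease assessment, if feasible. Section 8.2 also calls for scans when clinically indicated, and remote follow-up includes local practitioners and medical records, so progression found in routine care could be captured.
- **That the Study Calendar itself separates subjects by response.** Its Long-Term Follow-up cell is blank for responders as well. The dependence on response comes from 7.4 and the synopsis.

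It can also be said that Appendix V closes the best-response window at end of treatment. That fixes the response category; the documents set no such limit on SD duration. Finally, these endpoints are secondary and descriptive, without a hypothesis test. That limits the importance of the point but does not answer it.

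**Conclusion.** The contradiction is in the text and does not depend on any assumption. Its effect depends on which section a site follows. Under 7.4, an SD subject who stops without progression at or before about Cycle 7, with no dose delays, has no scheduled scan that can show 23 weeks of SD. Durable SD and CBR can then each be undercounted by 5 points per such subject in a cohort of 20. How many such subjects there will be cannot be derived from the documents.

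For PFS the conclusion is limited to lost information and inconsistent ascertainment by response status; no percentage can be supported. The primary safety objective is unaffected. This is an inexpensive correction that should be made before sites have to choose between the sections.

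**What to change.** Reconcile Section 7.4, the synopsis, Table 4 with its footnotes, and Section 8.2, so that everyone who discontinues without progression is assessed on one schedule with one stopping point:

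- In 7.4 and the synopsis, replace the responder-only wording with *Subjects who discontinue study treatment without PD (CR, PR or SD)*.
- In the same places, replace the two-month interval and the separate end point with a reference to the 8.2 schedule. Changing only who is covered would extend the existing conflict in interval and end point to SD subjects.
- In Table 4, mark disease assessment in the Long-Term Follow-up column for these subjects.
- In footnote s and 7.4, limit the remote allowance to survival contacts.

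The cost is wording, since 8.2 already requires the scans. The small downside is that sites which would have stopped scanning SD subjects must continue.

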#### 8.0 STUDY ASSESSMENTS

#### 8.1 Safety Assessments

#### 8.1.1 Safety Analysis

Safety data will be tabulated for all subjects and include vital signs, laboratory parameters, and AEs.

# 8.1.2 Reporting of Adverse Events

#### 8.1.2.1 Adverse Events

An AE is any untoward medical occurrence in a subject or clinical investigation subject administered a pharmaceutical product that does not necessarily have a causal relationship with the treatment. An AE can be any unfavorable and unintended sign (including a laboratory finding), symptom or disease temporally associated with the use of a medicinal (investigational) product, whether or not related to the medicinal (investigational) product.

The AE reporting period starts at study treatment initiation. At each evaluation, subjects should be interviewed in a non-directed manner to elicit potential adverse reactions from the subject. The occurrence of an AE will be based on changes in the subject's physical examination, laboratory results, and/or signs and symptoms.

All AEs (except Grade 1 and 2 laboratory abnormalities that do not require an intervention), regardless of causal relationship, are to be recorded in the eCRF and source documentation. The investigator must determine the intensity of any AEs according to the NCI-CTCAE version

5.0 and their causal relationship. Those AEs not covered by these criteria will be graded as follows:

- 1. Mild: Discomfort noticed, but no disruption of normal daily activity. Prescription drug not ordinarily needed for relief of symptom but may be given because of personality of subject.
- 2. Moderate: Discomfort sufficient to reduce or affect normal daily activity. Subject is able to continue in study; treatment for symptom may be needed.
- 3. Severe: Incapacitating, severe discomfort with inability to work or to perform normal daily activity. Severity may cause cessation of treatment with test drug; treatment for symptom may be given and/or subject hospitalized.
- 4. Life-Threatening: Symptom(s) place the subject at immediate risk of death from the reaction as it occurred; it does not include a reaction that, had it occurred in a more serious from, might have caused death.
- 5. Fatal: Event caused the death of the subject.

AEs will be followed until resolution or stabilization while the subject remains on-study. Once the subject is removed from study, events thought to be related to the study medication will be followed until resolution or stabilization, unless, in the investigator's opinion the event is unlikely to resolve due to the subject's underlying disease, or until the subject starts a new treatment regimen or the subject is lost to follow-up.

# 8.1.2.2 Attribution Definitions

The relationship of each AE to study treatment should be evaluated by the Investigator using the following criteria:

Definitely related: A clinical event, including laboratory test abnormality, occurring in a plausible time relationship to the medication administration, and which cannot be explained by concurrent disease or other drugs or chemicals. The response to withdrawal of the drug should be clinically plausible.

Possibly related: A clinical event, including laboratory test abnormality, with a reasonable time sequence to the medication administration, but which could also be explained by concurrent disease or other drugs of chemicals. Information on the drug withdrawal may be lacking or unclear.

Unlikely related: A clinical event, including laboratory test abnormality, with a little or no temporal relationship to medication administration, and which other drugs, chemicals or underlying disease provide plausible explanations.

Not related: A clinical event, including laboratory test abnormality that has no temporal relationship to the medication or has more likely alternative etiology.

# 8.1.2.3 Definition of an Unexpected Adverse Event

An unexpected AE is defined as any adverse drug experience, the specificity or severity of which is not consistent with the current IB; or, if an IB is not available, the specificity or severity of which is not consistent with the risk information described in this protocol or in the regulatory agency study authorization application.

Unexpected, as used in this definition, refers to an adverse drug experience that has not been previously observed (e.g., included in the IB) rather than from the perspective of such experience not being anticipated from the pharmacological properties of the pharmaceutical product.

# 8.1.2.4 Serious Adverse Event (SAE)

An SAE is defined as any untoward medical occurrence that at any dose:

- 1. Results in death,
- 2. Is life-threatening (i.e., the subject was at risk of death at the time of the event. It does not refer to an event which hypothetically might have caused death if it was more severe),
- 3. Requires inpatient hospitalization or prolongation of existing hospitalization excluding that for pain management, disease staging/re-staging procedures, or catheter placement unless associated with other serious events,
- 4. Results in persistent or significant disability/incapacity, or
- 5. Is a congenital anomaly/birth defect.

Important medical events that may not result in death, be life-threatening, or require hospitalization may be considered serious adverse drug events when, based on appropriate medical judgment, they may jeopardize the subject and may require medical or surgical intervention to prevent one of the outcomes listed above.

